### **9.3.2. Analytical Procedures**

Plasma samples will be analyzed to determine concentrations of ibrutinib and metabolite PCI-45227 using a validated, specific, and sensitive quantitative method by or under the supervision of the sponsor.

### **9.3.3. Pharmacokinetic Parameters**

Plasma concentrations of ibrutinib and metabolite PCI-45227 will be summarized using descriptive statistics. Based on the individual plasma concentration-time data, using the actual dose taken and the actual sampling times, PK parameters and exposure information of ibrutinib may be derived using population PK modelling, if it is deemed appropriate and if data allow.

## **9.4. Safety Evaluations**

The study will include the following evaluations of safety and tolerability according to the time points provided in the [TIME AND EVENTS SCHEDULE](#). Any clinically significant abnormalities persisting at the end of the treatment will be followed by the investigator until resolution, until a clinically stable endpoint is reached, or until the end of the study.

### **9.4.1. Adverse Events**

All adverse events will be reported from the time a signed and dated ICF is obtained until 30 days following the last dose of study drug. Adverse events will be reported by the subject (or, when appropriate, by a caregiver, surrogate, or the subject's legally acceptable representative) for the duration of the study. Adverse events will be followed by the investigator as specified in Section 12.

### **9.4.2. Clinical Laboratory Tests**

Blood samples for serum chemistry and hematology will be collected. The investigator must review the laboratory results, document this review, and record any clinically relevant changes occurring during the study in the adverse event section of the CRF. The laboratory reports must be filed with the source documents.

The following tests will be performed. See [TIME AND EVENTS SCHEDULE](#) for exact time points of these and other assessments.

- Hematology Panel (local laboratory)
  - hemoglobin
  - hematocrit
  - absolute neutrophil count
  - platelet count
  - total white blood cell (WBC) count
  - absolute lymphocyte count
- Serum Chemistry Panel (local laboratory)
  - albumin
  - ALT
  - calcium
  - creatinine
  - lactic acid dehydrogenase (LDH)
  - alkaline phosphatase
  - AST
  - blood urea nitrogen (BUN)
  - glucose
  - potassium

-phosphate	-total bilirubin
-sodium	-uric acid
-total protein	
• Coagulation (central laboratory)	
-PT/INR	-activated partial thromboplastin time
• Serum immunoglobulin (central laboratory)	
-IgG	-IgA
-IgM	
• $\beta$ 2 -microglobulin (central laboratory)	

Samples will be collected at Screening.

- Serum Viscosity (local laboratory)

Serum viscosity at Screening is optional. After Screening, it should be performed at the discretion of the treating physician in any subject with signs and symptoms suggesting a hyperviscosity syndrome.

- Hepatitis B Screening (local laboratory)
  - HBsAg
  - Hepatitis B core antibody

If HBsAg is positive, the subject will be excluded. Hepatitis B DNA needs to be performed if Hepatitis B core antibody is positive. DNA PCR needs to be confirmed negative prior to first dose of administration in subjects who are Hepatitis B core Ab positive. During study treatment and for at least 12 months following the last dose of treatment, regular monitoring of Hepatitis B PCR and liver enzymes and prophylactic antiviral medication should be considered per published guidelines.

- Hepatitis C Screening (local laboratory)
  - Hepatitis C antibody

If Hepatitis C antibody is positive, RNA PCR needs to be performed and confirmed negative prior to first dose administration. Patient with History of Hepatitis C virus infection should have documented 24 weeks of sustained virologic response (SVR) in order to be eligible for the study.

- Pregnancy Test (local laboratory)

For women of childbearing potential, serum will be drawn at screening for a pregnancy test. During the trial, if the subject is suspected of pregnancy, the pregnancy test must be performed. The pregnancy test will be done by the local laboratory.

#### **9.4.3.       Electrocardiogram (ECG)**

A 12- lead electrocardiogram (ECG) will be performed at screening for all subjects. The subject should be in a quiet setting without distractions (eg, television, cell phones). Subjects should rest in a supine position for at least 5 minutes before ECG collection and should refrain from talking

or moving arms or legs. Abnormalities noted at screening should be included in the medical history.

ECGs may also be performed at the investigator's discretion, particularly in subjects with arrhythmic symptoms (eg, palpitations, lightheadedness, syncope, chest discomfort or new onset of dyspnea).

#### **9.4.4. Vital Signs and ECOG Performance Status**

Vital signs (body temperature, heart rate, respiratory rate, and blood pressure) and ECOG Performance Status grade ([Attachment 2](#)) will be measured at the timepoints specified in the [TIME AND EVENTS SCHEDULE](#).

#### **9.4.5. Physical Examination**

The Screening, Week 1, Suspected PD, EOT and Follow-Up physical examination will include, at a minimum, the general appearance of the subject, height (screening only) and weight, and examination of the skin, eyes, ears, nose, throat, lungs, heart, abdomen, extremities, musculoskeletal system, nervous system, and lymphatic system. Only a limited symptom-directed physical examination and the change in status of lymph nodes, tumor masses, liver and spleen will be required after Week 1 at time points specified in the [TIME AND EVENTS SCHEDULE](#).

#### **9.4.6. Eye-related symptom assessment**

The subjects will be asked about eye-related symptoms at time points specified in the [TIME AND EVENTS SCHEDULE](#). If there are any eye-related symptoms of severity Grade  $\geq 2$  at Screening or if the subject develops any eye-related symptoms of severity Grade  $\geq 2$  while on study treatment, an ophthalmologic evaluation/consult must be performed and the outcome must be reported on the ophthalmologic eCRF.

### **9.5. Sample Collection and Handling**

The actual dates and times of sample collection must be recorded in the CRF or laboratory requisition form. Refer to the [TIME AND EVENTS SCHEDULE](#) for the timing and frequency of all sample collections.

Instructions for the collection, handling, storage, and shipment of samples are found in the laboratory manual that will be provided. Collection, handling, storage, and shipment of samples must be under the specified, and where applicable, controlled temperature conditions as indicated in the laboratory manual.

## **10. SUBJECT COMPLETION/DISCONTINUATION OF STUDY TREATMENT/ WITHDRAWAL FROM THE STUDY**

### **10.1. Completion**

A subject will be considered to have completed the study if he or she has died before the end of the study, has not been lost to follow-up, or has not withdrawn consent before the end of study.

The study is planned to be completed 3 years after the last subject receives first dose. The study drug will be supplied until study completion.

## **10.2. Discontinuation of Study treatment**

A subject will not be automatically withdrawn from the study if he or she has to discontinue study treatment before the end of the intervention regimen.

Study treatment will be discontinued in the event of any of the following events:

- Confirmed progressive disease
- Unacceptable toxicity: an intercurrent illness or adverse event that prevents further ibrutinib administration
- The subject refuses further treatment with the study drug
- Investigator decision (such as chronic noncompliance, significant protocol deviation, or best interest of the subject)
- The subject becomes pregnant

All subjects, regardless of reason for discontinuation of study treatment will undergo an EOT visit and be followed for progression and survival. The Investigator should notify the Sponsor within 24 hours if a subject discontinues ibrutinib treatment due to disease progression and should provide documentation of disease progression for review by the Sponsor's Medical Monitor. If a subject shows signs of disease progression on physical examination or laboratory assessment, the subject may continue study treatment until disease progression is confirmed. These subjects should stay in the study to be followed for survival.

## **10.3. Withdrawal From the Study**

A subject will be withdrawn from the study (including all follow-up) for any of the following reasons:

- Lost to follow-up
- Withdrawal of consent
- Study termination by Sponsor
- Death

If a subject is lost to follow-up, every reasonable effort must be made by the study-site personnel to contact the subject and determine the reason for discontinuation/withdrawal. The measures taken to follow up must be documented.

When a subject withdraws before completing the study, the reason for withdrawal is to be documented in the CRF and in the source document. Study drug assigned to the withdrawn subject may not be assigned to another subject. Additional subjects will not be entered. If a subject discontinues study drug and withdraws from the study, EOT and posttreatment

assessments should be obtained, if possible. If the reason for withdrawal from the study is withdrawal of consent then no additional assessments are allowed.

## **11. STATISTICAL METHODS**

Statistical analysis will be done by the sponsor or under the authority of the sponsor. A general description of the statistical methods to be used to analyze the efficacy and safety data is outlined below. Specific details will be provided in the Statistical Analysis Plan.

The primary analysis for all efficacy and safety endpoints will be conducted 12 months after last subject receives first dose or alternative appropriate cutoff will be considered based on regulatory requirement. Final analysis will be conducted at the study end.

Analysis of efficacy will be performed using the All-Treated Population. The 90% CIs for the ORR, CRR and rate of VGPR or better will be calculated using exact binomial distribution. Exact (Clopper-Pearson) 90% CIs will be presented. Time to-event variables (including DOR, PFS and OS) will be described using the Kaplan-Meier method. Time to response will be summarized descriptively for responders only. Unless otherwise specified, all continuous endpoints will be summarized using descriptive statistics, which will include the number of subjects with a valid measurement (n), mean, standard deviation, median, minimum, and maximum. All categorical endpoints will be summarized using frequencies and percentages.

### **11.1. Subject Information**

The following definitions will be used for the efficacy, safety and PK analysis, respectively:

All Treated population: All enrolled subjects who receive at least 1 dose of study drug.

Safety population: All enrolled subjects who receive at least 1 dose of study drug. The safety population is identical to All Treated population.

PK evaluable population: All enrolled subjects who receive at least 1 dose of ibrutinib and have at least 1 available PK sample after treatment.

### **11.2. Sample Size Determination**

Assuming the ORR (PR or better) by investigator is 69.8% in the study population, which is the same as global pivotal study (PCYC-1118E) result, approximately 17 subjects will be required to obtain at least 85% power to declare the ORR is 32% (the minimum clinically meaningful ORR) or higher at the 1-sided significance level of 0.05.

### **11.3. Efficacy Analyses**

For continuous variables, number of observations, means, standard deviations, medians, and ranges will be included. For categorical variables, frequency and percentage will be summarized. For time-to-event variables, Kaplan-Meier estimates will be provided.

### **11.3.1. Primary Efficacy Endpoint**

The primary efficacy endpoint is ORR by investigator assessment. ORR is defined as the proportion of subjects who achieve PR or better per the modified Consensus Response Criteria from the VIth IWWM (NCCN 2019).

The overall response rate (PR or better) and its 90% CI will be calculated with the exact test for binomial distribution in the All Treated population. The study is considered to be positive if the lower limit of the exact 2-sided 90% CI based on binomial distribution exceeds the threshold value (0.32).

### **11.3.2. Secondary Efficacy Endpoints**

#### **11.3.2.1. Clinical Response Rate**

CRR is defined as the proportion of subjects who achieve MR or better according to the modified IVth IWWM (NCCN 2019) criteria as assessed by the investigator. CRR will be analyzed with the exact 2-sided 90% CI based on binomial distribution in a similar fashion as ORR.

#### **11.3.2.2. VGPR or Better Rate**

VGPR or better rate is defined as the proportion of subjects who achieve VGPR or better according to the modified IVth IWWM (NCCN 2019) criteria as assessed by the investigator. VGPR or better rate will be analyzed in a similar fashion as CRR.

#### **11.3.2.3. Duration of Response**

DOR is defined as duration from the date of initial documentation of a response (PR or better) to the date of first documented evidence of progressive disease or death for responders (PR or better) as assessed by the investigator. DOR will be evaluated descriptively using Kaplan-Meier method. Median DOR and the corresponding 95% CI will be provided if estimable with Kaplan-Meier plot.

#### **11.3.2.4. Time to Response**

Time to response (TTR) is defined as the time from the date of first dose to the date of initial documentation of a response (PR or better). TTR will be summarized by descriptive statistics.

#### **11.3.2.5. Progression Free Survival**

PFS is defined as duration from the date of first dose to the date of disease progression or death, whichever is first reported, assessed according to the modified VIth IWWM (NCCN 2019) criteria. PFS will be evaluated descriptively using Kaplan-Meier method. Median PFS and the corresponding 95% CI will be provided if estimable with Kaplan-Meier plot. PFS rates at 1-year, 2-year and 3-year landmarks will also be estimated using Kaplan-Meier.

#### **11.3.2.6. Overall Survival**

OS is measured from the date of first dose to the date of the subject's death from any cause. The OS will be evaluated in a similar fashion as DOR and PFS.

## 11.4. Pharmacokinetic Analyses

The plasma concentration data for ibrutinib and metabolite PCI-45227 at each timepoint will be listed and summarized using descriptive statistics. All concentrations below the lowest quantifiable concentration or missing data will be labeled as such in the concentration data listing. Concentrations below the lowest quantifiable concentration will be treated as zero for the population PK modeling, if needed. All subjects and samples excluded from the analysis will be clearly documented in the study report.

If feasible, population PK analysis of ibrutinib may be performed using nonlinear mixed-effects modeling (NONMEM). Data may be pooled with other ibrutinib trials if appropriate. Model-derived exposure parameters may be subjected to further explore correlation between exposure and relevant clinical information.

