### **1.1.2.1. Human Pharmacokinetics**

The PK of ibrutinib has been assessed in subjects with B-cell malignancies, cGVHD, as well as in healthy subjects. In all studies, both parent ibrutinib and metabolite PCI-45227 were quantified. PCI-45227 is a prominent dihydrodiol metabolite observed in laboratory animals and humans, with a reversible inhibitory activity towards BTK approximately 15 times lower than that of ibrutinib and with plasma concentrations in the same range as parent drug levels. The on target effects of metabolite PCI-45227 are not considered clinically relevant. The PK of ibrutinib does not significantly differ in patients with different B-cell malignancies (CLL, SLL, MCL, WM, and MZL). Ibrutinib is absorbed after oral administration with a median  $T_{max}$  of 1 hour to 2 hours. The half-life of ibrutinib is 4 to 6 hours. Administration of ibrutinib in a fasted condition resulted in approximately 60% of exposure (AUC) as compared to administration either in fed condition (30 minutes after a high-fat breakfast), or 2 hours after a meal. Considering the approximate doubling in mean systemic exposure when dosed with food and the favorable safety profile, ibrutinib can be dosed with or without food. The PK in Chinese CLL/SLL patients is similar to those in non-Chinese subjects with various B-cell malignancies.

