## 3. STUDY DESIGN AND RATIONALE

### 3.1. Overview of Study Design

This is a single-arm multicenter, Phase 4 study to evaluate the efficacy and safety of ibrutinib in Chinese subjects with relapsed or refractory WM with symptomatic disease meeting at least 1 of the recommendations from the Second IWWM for requiring treatment.

Approximately 17 subjects will be enrolled into the study. Subjects will receive ibrutinib 420 mg daily until disease progression or unacceptable toxicity, whichever occurs first. Ibrutinib will be supplied as hard gelatin capsules for oral administration.

The study will include a Screening Phase, a Treatment Phase and a Follow-Up Phase.

The Screening Phase assessments will be performed within 30 days prior to study treatment and will begin on the day the subject signs informed consent. During the Screening Phase, the subjects' eligibility will be determined.

The Treatment Phase will extend from first dose of study drug until study drug discontinuation.

[figure not shown]
The Follow-up Phase will consist of the Post-treatment pre-disease progression Phase and a Post-disease Progression Phase. The Post-treatment pre-disease progression Phase will extend from the discontinuation of treatment (for reasons other than disease progression) until the subject has progressive disease, at which point the Post-disease Progression Phase will begin. Subjects who progress on treatment will transition directly to the post disease progression phase. In this latter phase, subsequent anticancer therapy, occurrence of any other malignancy and survival status will be recorded until death, lost to follow-up, consent withdrawal, or study closure.

The study is planned to be completed 3 years after the last subject receives first dose.

Clinical cutoffs (CCOs) planned for this study are:

- CCO for the primary analysis is estimated to be performed approximately 12 months after the last subject receives first dose. Alternative appropriate cutoffs will be considered based on regulatory requirement.
- CCO for the final analysis is estimated to occur 3 years after last subject receives first dose.

A diagram of the study design is provided in [Figure 1](#).

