#### **6. DOSAGE AND ADMINISTRATION**

Ibrutinib will be administered orally, once daily, at a dose of 420 mg (140 mg × 3 capsules taken together at one time). Protocol-specified dose modifications of ibrutinib will be made as

necessary. Study drug (3 capsules) is administered orally once daily with approximately 8 ounces (240 mL) of water. The capsules should be swallowed whole and should not be opened, broken, or chewed. The use of strong CYP3A inhibitors/inducers, and grapefruit and Seville oranges should be avoided for the duration of the study (Section 8.2 and Attachment 3).

If a dose is not taken at the scheduled time, it can be taken as soon as possible on the same day with a return to the normal schedule the following day. The subject should not take extra capsules to make up the missed dose. Missed doses of study drug will not be made up.

The first dose will be administered in the clinic on Day 1 of Week 1, after which study drug will be self-administered daily by the subjects on an outpatient basis. Study drug will be dispensed to subjects in bottles. Unused study drug dispensed during previous visits must be returned to the site and drug accountability records (Section 14.5) updated at each visit. Returned capsules must not be re-dispensed to anyone.

Study drug dosing is continuous (without interruptions) throughout the Treatment Phase.

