## **9.3. Pharmacokinetics**

### **9.3.1. Evaluations**

Venous blood samples of approximately 2 mL will be collected from all subjects for measurement of plasma concentrations of ibrutinib and metabolite PCI-45227 before dosing ibrutinib capsules on Day 1 of Weeks 1, 5, and 9 (see [TIME AND EVENTS SCHEDULE](#)).

Subjects should refrain from taking the study drug on the morning of study visits designated for PK sampling. After PK sampling, the study drug will be self-administered by the subjects on an outpatient basis, except for Day 1 of Week 1, when the study drug will be administered in the clinic. The exact dose, dates and times for the doses administered 1 day preceding and actual PK sampling dates and times must be recorded. Additional information about the collection, handling, and shipment of biological samples can be found in the Laboratory Manual.

Samples collected for PK analyses may additionally be used to evaluate safety or efficacy aspects that address concerns arising during or after the study period.

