## 7. PHARMACOKINETICS

Pharmacokinetic evaluable analysis set will be used for PK analyses. The individual plasma concentration data of ibrutinib and its metabolite PCI-45227 will be listed and graphically displayed (linear scale and/or semi-log scale). Concentrations below the lowest quantifiable concentration or missing data will be labeled as such in the concentration data presentation. The data will be summarized at each timepoint using descriptive statistics (mean, standard deviation [SD], coefficient of variation, median, minimum and maximum) and will be graphically displayed if possible. Concentration data below the lowest quantifiable concentration will be treated as zero in the summary statistics.

Subgroup analysis by ibrutinib dose and concomitant CYP3A inhibitors may be performed on the individual pre-dose plasma concentration at Week 5 Day 1 and Week 9 Day 1 of ibrutinib and PCI-45227. Necessity of subgroup analysis will be determined based on the actual number of subjects who received concomitant CYP3A inhibitors and/or dose reduction till the pre-dose of Week 9 Day 1. Summary tables and visual comparisons may be provided to present the summary statistics derived for each subgroup, if possible. The visual comparisons graphical presentation may also be performed for dose-normalized pre-dose plasma concentration of ibrutinib at Week 5 Day 1 and Week 9 Day 1 regardless of ibrutinib dose.

Additional analyses may be performed as deemed necessary.

Based on the individual plasma concentration-time data, using the actual dose taken and the actual sampling times, PK parameters and exposure information of ibrutinib may be derived using population PK modelling, if it is deemed appropriate and if data allow.

For concentration summary, applying the following rules.

- When more than half (>50%) of concentration data are BQL at each scheduled time point, mean and median will be reported as 'BQL'; SD and %CV are reported as 'NC'; maximum and minimum will be reported as observed (including BQL).
- When number of concentration data are equal to or less than 2, SD, %CV, median, minimum and maximum will be shown as 'NC' regardless of the proportion of BQL.

Data or subjects will be excluded from the analysis if the data do not allow for accurate assessment of the PK. All subjects and samples excluded from the analysis will be clearly documented in the study report.

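### Protocol 11.4 sets post-dose below-limit concentrations to zero in the optional population PK model, which would bias exposure downward if such values are frequent

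*Protocol*

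**What the plan says.** Protocol 11.4 fixes how BQL values enter the model: "Concentrations below the lowest quantifiable concentration will be treated as zero for the population PK modeling, if needed". The model itself is conditional on feasibility, may be pooled with other ibrutinib trials, and may feed an exploration of exposure against clinical information.

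SAP section 7 also keeps the model as an option but has no BQL rule for it. Its zero rule is for a different purpose: "Concentration data below the lowest quantifiable concentration will be treated as zero in the summary statistics". Its further rule, which reports the mean and median as BQL when more than half the values at a time point are BQL, also covers only the concentration summaries.

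Under Protocol 9.3.1, samples are taken "before dosing ibrutinib capsules on Day 1 of Weeks 1, 5, and 9", and "Subjects should refrain from taking the study drug on the morning of study visits designated for PK sampling". Protocol section 6 sets the dosing interval: "Ibrutinib will be administered orally, once daily, at a dose of 420 mg". Protocol 1.1.2.1 gives the elimination: "The half-life of ibrutinib is 4 to 6 hours".

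**The concern.** A post-dose BQL result lies somewhere between zero and the LLOQ. Entering it as an exact zero tells the model that the drug has gone, so the error always runs in the same direction: troughs too low, elimination too fast, spread between subjects too wide.

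The design leaves little to offset this. The Week 1 sample precedes any drug, so every sample from this study that carries drug information is a trough. With no sample near the peak, AUC and Cmax can come only from a model. PK in Chinese subjects is a secondary objective. What is at stake is therefore the model-derived exposure and any later correlation with clinical information, if those analyses are done.

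**Working it through.** **Inputs from the documents.** Half-life 4 to 6 h (Protocol 1.1.2.1); once-daily dosing (Protocol 6); predose sampling at Weeks 1, 5 and 9 with the morning dose withheld (Protocol 9.3.1); about 17 subjects (Protocol 3.1).

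**Not in the documents.** The LLOQ, the expected BQL fraction, the trough variability and the error model. These are assumed below. The plan states no figure on this point to reproduce.

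**Step 1: how low the troughs are.** Once-daily dosing gives a nominal 24 h since the last dose. That is 24/6 = 4 to 24/4 = 6 half-lives. The fraction left is 2^(−24/t½): 2^(−4) = 6.25% at 6 h and 2^(−6) = 1.56% at 4 h. This makes BQL values plausible. It does not give their frequency, which also needs the starting concentration and the LLOQ. The metabolite's half-life is not given, so this covers the parent drug only.

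**Step 2: how much data.** 17 subjects × 2 on-treatment samples = about 34 informative values.

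**Step 3: effect on the model.** Simulated steady-state trough: C = C0·e^(−24k)/(1 − e^(−24k)), with typical k = ln 2/5 per hour. Assumptions:
- 20% between-subject variability on k and 25% proportional error;
- additive error of 0.5 or 0.2 × LLOQ, held fixed;
- C0 held fixed, no pooling;
- LLOQ placed to give the nominal BQL fraction (set before the additive error is added, so realised fractions are approximate);
- 17 subjects × 2 troughs, 60 replicates per setting, fitted by maximum likelihood with quadrature.

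With predicted trough m and residual SD s, zero substitution contributes the normal density at 0. The censored (M3) fit contributes the probability of falling below the limit, Φ((LLOQ − m)/s).

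Median results, with additive error of 0.5 and then 0.2 × LLOQ:

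| BQL fraction | Bias in k, zero | Bias in typical trough, zero | Between-subject SD, zero (true 0.20) | Bias in k, M3 |
|---|---|---|---|---|
| 5% | −0.2%, +0.8% | +1%, −3% | 0.18, 0.20 | −0.3%, +0.1% |
| 10% | +0.1%, +2.5% | 0%, −8% | 0.21, 0.21 | −1.0%, +0.5% |
| 30% | +4.6%, +9.2% | −15%, −27% | 0.23, 0.31 | −0.5%, −0.6% |
| 50% | +9.6%, +20.7% | −28%, −51% | 0.27, 0.44 | +0.4%, −2.4% |

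Fits to the same data with no censoring had a bias in k of up to 2.0% in either direction. The M3 fits are therefore within about the noise of the exercise, and the zero fits at 30% and above are not.

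**Step 4: what this does to AUC.** With C0 fixed, AUC over a dosing interval is C0/k, so its bias is 1/(1 + bias in k) − 1. At 30% BQL: 1/1.046 − 1 = −4.4% to 1/1.092 − 1 = −8.4%. At 50%: 1/1.096 − 1 = −8.8% to 1/1.207 − 1 = −17.1%.

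**Step 5: a separate quantity.** For log-normal troughs with the lowest fraction f set to zero, the bias of the arithmetic mean is −Φ(z_f − σ), with σ² = ln(1 + CV²). At CV 100%, σ = 0.833. At f = 30%, z_f = −0.524 and the bias is −Φ(−1.357) = −8.7%; at f = 50% it is −Φ(−0.833) = −20.3%. These figures describe the SAP's summary-statistics rule. They are not evidence of bias in model parameters.

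**The case against.** The strongest reply is that the criticised sentence may never be used. The model depends on feasibility, the zero rule applies only if needed, and the firm deliverable is a descriptive summary of concentrations. Thirty-four troughs say little about elimination or Cmax on their own. A feasible model would probably borrow from other trials or fix some parameters, and Protocol 11.4 allows pooling. Pooling would dilute the bias, so an unpooled simulation is an unfavourable case. Protocol 9.3.2 also requires a sensitive assay. All of this stands and limits the size. It does not make zero the right value for a post-dose BQL result.

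Some zeros are right. The Week 1 sample precedes the first dose, and Protocol 4.2 excludes prior ibrutinib exposure. A blanket censoring rule would be wrong for those samples.

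A reader might infer more than the documents support:
- *That BQL values are likely.* A small fraction left at 24 h cannot establish this without the LLOQ and the concentration level.
- *That zero makes the model undefined.* This holds for a log-transformed model. Under proportional error a zero is computable, though it forces a −100% residual. Neither document specifies an error model.
- *That biased exposures will be correlated with outcome.* Protocol 11.4 only permits that exploration.

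**Conclusion.** The point holds as a conditional, minor one. As written, the plan would put a known wrong value into the model for every post-dose BQL sample, and nothing in the SAP replaces the rule. If such values are frequent and the data are modelled largely alone, elimination is overstated, exposure understated and between-subject variability inflated. The bias in the elimination rate is negligible at about 5% BQL, about 5 to 9% at 30% and 10 to 21% at 50%.

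Those sizes rest on a 5 h half-life, the variability and error assumptions in step 3, a fixed initial concentration and no pooling. The BQL fraction itself cannot be fixed from the documents. The claim that this trial's PK results will be biased is therefore not supported; the claim that the rule risks it is. ORR and the success rule do not depend on it.

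**What to change.** Replace the sentence in Protocol 11.4, and put the same text in SAP section 7:

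> Post-first-dose BQL observations will be treated as left-censored by likelihood (M3 method) in any population PK model, or omitted with a sensitivity check if the BQL fraction is small. Week 1 predose samples taken before first exposure will not be treated as censored observations. The LLOQ and BQL fraction will be reported.

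The labelling of BQL values in the listings stays as it is. The change needs no new samples, subjects or data. It costs a short text edit in each document and slightly more modelling effort and run time.
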